Title: Clinical and Radiographic Evaluation of Formocresol, Ferric Sulfate and Hyaluronic Acid Pulpotomies on Human Primary Teeth: A Randomized Controlled Clinical Trial

NCT Number: NCT04115358

Document Date: 01/09/2019

Study Protocol and Statistical Analysis Plan

In this study, 120 primary molar teeth from healthy children aged between 5 and 9 and who apply to Marmara University Faculty of Dentistry Department of Pediatric Dentistry will be subjected to pulpotomy treatments. Ethical approval of the study was obtained from the Clinical Research Ethics Committee, Faculty of Dentistry at Marmara University (No: 2019/288) in accordance with the Declaration of Helsinki. Sample size calculation showed that at first 40 teeth in each group will be required to detect a significant difference (80% power, two-sided 5% significance level). After proper diagnosis of coronal pulpitis, the teeth will be assigned randomly to one of the 3 groups: 40 primary molars for formocresol pulpotomy treatments, 40 primary molars for ferric sulfate treatments and 40 primary molars for 0.5% hyaluronic acid gel pulpotomy treatments. The tooth decay will be removed, the pulp will be amputated from the chamber of the pulp with a sharp excavator and one of the medicament will be applied to the orifice of the root canals. The cavity will be sealed tight with zinc oxide cement and the primary molars will be restored either with a composite filling material in case of occlusal cavities or with a stainless-steel crown in case of proximal cavities. A single investigator will perform the procedure. The teeth will be followed clinically and radiographically at 1st, 3rd, 6th, 12th months.

Statistical analyzes in this study will be performed using the NCSS (Number Cruncher Statistical System) 2007 Statistical Software (Utah, USA) packaged software. In the evaluation of the data, in addition to descriptive statistical methods (mean, standard deviation, frequency and percentage distributions), the distribution of variables will be examined with the Shapiro-Wilk normality test, the independent t test for the comparison of the normally distributed variables in binary groups, the chi-square and Fisher exact test for the comparison of qualitative data, Mc Nemar's test will be used for time comparisons of qualitative data. The results will be evaluated at the significance level of $p<0.05$.

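### Teeth are assigned before decay removal and pulp amputation, although the arms differ only at the medicament, so the operator may know the arm during shared steps

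*Combined protocol and SAP*

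**What the plan says.** All of this is in the first paragraph under Study Protocol and Statistical Analysis Plan in the combined document.

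- Trigger for allocation: "After proper diagnosis of coronal pulpitis, the teeth will be assigned randomly to one of the 3 groups".
- Next, the operative steps common to all teeth: "The tooth decay will be removed, the pulp will be amputated from the chamber of the pulp with a sharp excavator".
- Then the first step that differs by arm: "one of the medicament will be applied to the orifice of the root canals".
- Operator: "A single investigator will perform the procedure".
- Sample size: "Sample size calculation showed that at first 40 teeth in each group will be required to detect a significant difference", at "80% power, two-sided 5% significance level". The number assigned is also 40 per group, with no stated allowance for exclusions or loss.

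The paragraph does not say when the operator learns the assignment, whether it is concealed, or whether anyone is blinded. It gives no suitability check during the procedure, no rule for a tooth found unsuitable after assignment, and no analysis population.

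**The concern.** Randomisation protects the comparison best when nothing that can be influenced by the operator, and that all arms share, lies between opening the assignment and the point where treatments diverge. Here two operative steps lie in that gap, and the second exposes the pulp, whose condition is the basis for entry. New information on whether the tooth belongs in the trial can therefore arise after it has been assigned.

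Two things are at stake. If the operator knows the arm, the conduct of decay removal and amputation could differ by arm before the treatments do. And a decision to drop, replace or keep a tooth could be made with knowledge of its arm. If such decisions differ between arms, the groups stop being comparable. Even if they do not, dropped teeth reduce the 40 per arm on which the stated power rests.

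**Working it through.** **Order of events.** The text runs: diagnosis, random assignment, decay removal, amputation, medicament. The word placing assignment after diagnosis is an explicit time marker, and nothing stated delays the assignment further. Nothing between assignment and medicament depends on the arm. Assignment could therefore be opened after amputation without changing any treatment.

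**The plan's own figure.** The 40 per group cannot be reproduced, because no success rates, effect size or dropout are given. Solving backwards at 80% power and two-sided 5%, without continuity correction, 40 per group would detect 99% against about 80%, 95% against about 72%, or 90% against 64%. These pairs are assumptions and only anchor the power figures below.

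**Power if assigned teeth are lost.** Take 40 as exactly sufficient for 80% power and let a proportion d of each arm be dropped (d assumed):

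power = Φ[(1.960 + 0.842)·√(1 − d) − 1.960]

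- d = 5%, 38 teeth left: Φ(2.802 × 0.9747 − 1.960) = Φ(0.771) = 78.0%.
- d = 10%, 36 teeth left: Φ(2.802 × 0.9487 − 1.960) = Φ(0.698) = 75.7%.

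The back-solved pairs of proportions give the same to within about 0.1 point.

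**Selective exclusion, worst case.** All inputs except the 40 per arm are assumed. A share q of teeth look advanced on opening and fail with probability h; the rest fail with probability l; there is no true arm difference. One arm keeps all 40 teeth and has failure rate qh + (1 − q)l. The other drops every advanced-looking tooth, leaving 40(1 − q) teeth with failure rate l. The spurious difference is

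qh + (1 − q)l − l = q(h − l).

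For example, q = 10%, h = 60%, l = 10% gives 0.10 × 0.50 = 5 points.

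The false-positive rate is found by enumerating all outcomes of the two binomials and adding the probabilities of those with p < 0.05. The plan names both chi-square and Fisher's exact test, so both are shown. Ranges are over (h, l) = (50%, 10%), (60%, 10%), (40%, 5%) and (50%, 5%).

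| q | Teeth left in the dropping arm | Spurious difference (points) | False positives, Pearson (uncorrected) | False positives, Fisher |
|---|---|---|---|---|
| 5% | 38 | 1.8-2.5 | 5.3-6.2% | 1.2-3.4% |
| 10% | 36 | 3.5-5.0 | 6.0-8.9% | 2.9-5.8% |
| 15% | 34 | 5.3-7.5 | 11.0-16.0% | 5.7-10.2% |
| 20% | 32 | 7.0-10.0 | 13.5-20.7% | 10.2-16.4% |

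With no differential exclusion (both arms n = 40, both with failure rate qh + (1 − q)l), the same enumeration gives 5.1-5.9% for Pearson and 0.8-2.8% for Fisher. Fisher therefore stays near or below 5% up to q = 10% largely because it starts well below 5%. The spurious difference itself does not depend on the test.

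**The case against.** A reader might infer two stronger things, and the document supports neither.

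The first is that the operator does know the arm throughout. The text does not say so. Generating an assignment is not the same as disclosing it, and a sealed allocation could be opened only at the medicament step. A one-paragraph narrative is also weak evidence of an exact schedule, and the plan does not define which examinations make up the diagnosis. This stands: arm knowledge is a possibility the plan leaves open. It does not remove the point, because the only stated trigger is diagnosis and no delay or concealment is described.

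The second is that teeth found unsuitable become post-randomisation exclusions. No exclusion rule is given, nor who would decide. Such teeth could equally be kept and analysed as assigned, in which case the power loss disappears. This also stands. The plan simply leaves all three outcomes open.

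On size, complete one-sided exclusion is an extreme that nothing in the document suggests will happen. Partial or equal exclusion would do less. At 5-10% of teeth, false-positive rates stay close to nominal with Pearson and near or below it with Fisher. The power loss is 2-4 points and stems as much from the absence of any attrition allowance, a separate matter. Finally, an analyse-as-assigned rule with a stated disclosure time would meet much of the concern without moving randomisation. That is fair, but it would leave unsuitable teeth in the comparison, which late opening avoids.

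**Conclusion.** The point holds as a cheap design improvement, not as a demonstrated error. As written, assignment precedes two steps that all arms share, and nothing stated keeps the single operator from knowing the arm during them or when judging the opened tooth.

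The size depends wholly on assumed rates. Losing 5-10% of assigned teeth takes 80% power to about 76-78%. Under complete one-sided exclusion, false-positive inflation is small at 5-10% of teeth and becomes material at about 15-20%, where the spurious difference is 5-10 points and the false-positive rate about 11-21% (Pearson) or 6-16% (Fisher). These are upper figures for the chosen failure rates. The case for the change rests on the order of steps and the low cost, not on these figures.

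**What to change.** Replace the allocation sentence with wording such as: *After diagnosis, decay removal and amputation of the coronal pulp, and once the operator has recorded that the tooth still meets the trial's eligibility criteria, the next concealed assignment will be opened and the assigned medicament applied.*

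Add two rules. Teeth found unsuitable before that point are logged as not randomised and do not count toward the 40 per arm. Every tooth whose assignment is opened is analysed in its assigned arm. The eligibility criteria are the trial's own and need to be written down where they are not already, as does the method of concealment.

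The cost is a few sentences, plus opening an assignment mid-procedure with all three medicaments ready at the chairside. No extra visits, staff or analysed teeth are needed, and the target of 40 per arm is unchanged. If the site already works this way, only the text changes.

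### Does letting cavity type decide the final restoration, with no stratification and only unadjusted tests, undermine the comparison of the three medicaments?

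*Combined protocol and SAP*

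**What the plan says.** The first paragraph of the Study Protocol and Statistical Analysis Plan makes the final restoration depend on the cavity: teeth are "restored either with a composite filling material in case of occlusal cavities or with a stainless-steel crown in case of proximal cavities". The rule does not mention the medicament. On allocation, the paragraph says that "the teeth will be assigned randomly to one of the 3 groups", with 40 primary molars in each, and it names no stratification factor. On size, it says that "at first 40 teeth in each group will be required to detect a significant difference (80% power, two-sided 5% significance level"; no success rates or effect size are given.

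The second paragraph names the between-group tests. For categorical outcomes it lists "the chi-square and Fisher exact test for the comparison of qualitative data". No stratified test, regression model or covariate appears. McNemar's test is reserved for comparisons over time, so it does not adjust the group comparison.

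**The concern.** Two different restorations are used, and a pulpotomized tooth might do better or worse depending on which one it receives or on the kind of cavity that led to it. If one medicament group had many more proximal cavities than another, part of the difference in success could reflect cavity type instead of the medicament. With 40 teeth per group and no stated stratification, some imbalance is likely. With no adjustment fixed in advance, any later adjustment would be chosen after the results were known. At stake would be a biased comparison, a wrong error rate or a meaningful loss of power. Each can be checked.

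**Working it through.** **1. Is there bias?** Cavity type is a property of the tooth and exists before allocation. The restoration rule is the same in every group. Random allocation therefore makes the expected cavity mix equal across groups, and the restoration cannot carry a systematic difference between medicaments. Only chance imbalance remains.

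**2. The plan's own figure.** Forty per group cannot be reproduced, because the effect size is not stated. It can be solved backwards for two proportions at 80% power and two-sided 5%:

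n = [1.96·√(2p̄(1−p̄)) + 0.842·√(p₁(1−p₁) + p₂(1−p₂))]² / (p₁−p₂)²

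For 0.95 v 0.72, p̄ = 0.835 and n = (1.96 × 0.525 + 0.842 × 0.499)² / 0.23² = 1.449² / 0.0529 = 39.7, so 40. For assumed better-group success rates from 0.99 down to 0.80, the detectable difference is about 19 to 29 points.

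**3. Size of chance imbalance.** The proximal share is not in the document; 30-90% is assumed. With M proximal teeth among 120 split into three groups of 40, the variance of the difference in counts between two groups is (2/3)·M(120−M)/119.

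- M = 60 (50%): (2/3) × 3600/119 = 20.2, SD 4.49 teeth, or 11.2 points.
- M = 36 or 84 (30% or 70%): (2/3) × 3024/119 = 16.9, SD 4.12 teeth, or 10.3 points.

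The median absolute imbalance for a pair of groups is 7.5 points at 30-70% proximal and 5 points at 90%. A given pair differs by 20 points or more in 9.4% of randomisations at 50% proximal, about 7% at 30% or 70%, and 0.4% at 90%.

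**4. Resulting shift in the group difference.** Shift = imbalance × failure gap between cavity types. The document does not say there is a gap; 10-20 points is assumed.

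| Imbalance | Gap 10 points | Gap 20 points |
|---|---|---|
| 7.5 points (median) | 0.75 | 1.5 |
| 20 points | 2 | 4 |

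**5. Does the crude test already allow for this?** Yes. Take 50% proximal and failure of 5% v 25%, hence 15% overall. The crude variance of a group difference is 2 × 0.15 × 0.85/40 = 0.006375 (SE 8.0 points). The part due to cavity mix is 2 × 0.5 × 0.5 × 0.20²/40 = 0.0005 (SD 2.2 points), which is 7.8% of the total and already inside it. The chance imbalance is therefore counted in the ordinary standard error.

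**6. Type I error.** In simulated three-arm trials at 30-70% proximal, chi-square rejected in 4.3-5.0% and a Cochran-Mantel-Haenszel (CMH) test stratified by cavity type in 4.4-4.9%. There is nothing to correct.

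**7. Power.** CMH minus chi-square, three arms, one arm worse by 25 points, 30-90% proximal, where chi-square power is about 67-87% (near the planned 80%):

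| Failure gap between cavity types | Change in power (points) |
|---|---|
| none | about -0.9 to -0.1 |
| 10 points | about -1.0 to +0.6 |
| 20 points | about -0.1 to +2.3 |

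A two-arm check at success 0.90 v 0.65 agrees. Power is 0.79-0.80 for both simple allocation with chi-square and stratified allocation with CMH at a gap of 5-10 points. At a 20-point gap it rises from 0.79 to 0.81-0.82.

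**The case for a change.** The strongest case for acting is practical. At 30-70% proximal, at least one of the three pairs of groups differs by 20 points or more in proximal share in about 16-22% of randomisations. A reader of the results would then ask for an adjusted analysis, which would have been chosen after the fact. A sentence written now would prevent that, and the operator must establish cavity type anyway to choose the restoration. Larger power gains can also be found: +5.2 points for CMH over chi-square, and up to +7.8 points for an exact stratified test over Fisher.

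Part of this stands. The plan is silent on cavity type, recording and tabulating it by group would be informative, and a pre-specified adjusted analysis would be legitimate.

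The rest is weaker than it looks. The +5.2 arises in one corner: 30% proximal, failure of 5% v 25%, and an odds-ratio alternative in which chi-square has only about 48% power, well below the planned 80%. The exact-test gains matter only when failures are few. If the exact version is reserved for fewer than 15 failures in total, it would be used in 0-8% of trials under the alternatives with a 20-point gap. About 1-3 points of those gains appear even when cavity type has no effect, so they come from a less discrete test.

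The change is also more than a sentence. It needs a definition of success, a chosen time point (the plan says only that "The teeth will be followed clinically and radiographically at 1st, 3rd, 6th, 12th months"), a multiplicity order, a switch to an exact test and a check of what the software named in the second paragraph can do. Cavity type would have to be classified before assignment, whereas decay removal is described after it. Stratified allocation in blocks of 3 and 6 could leave two groups up to 4 teeth apart. Finally, the risk of after-the-fact adjustment presumes a departure from the plan, which already names the unadjusted tests.

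**Conclusion.** The concern does not hold. One restoration rule, driven by the tooth and applied in every group, does not confound a randomized comparison of medicaments, and the planned unadjusted tests keep their error rate. The shift from chance imbalance is 0.75-1.5 points at the 7.5-point median and 2-4 points at a 20-point imbalance, against a detectable difference of about 19-29 points. The power effect of stratifying the test, about -1.0 to +2.3 points near the planned power, changes sign with the assumed proximal share and failure gap. Whether to adjust is a matter on which competent statisticians may differ.

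The figures assume 30-90% proximal cavities (30-70% for the type I error), a failure gap of 0-20 points for power and 10-20 points for the shift, and independent teeth. The document supplies neither the cavity mix nor the gap. The conclusion on bias needs none of these assumptions; it rests on random allocation and a common restoration rule. The missing effect size, primary endpoint and allocation method, and the handling of several teeth from one child, are separate questions that this conclusion does not settle.

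### Every result is judged at p<0.05 across three arms, two domains and four visits, with no primary outcome, visit, contrast or multiplicity rule, so the chance of a false medicament difference is not held at 5%.

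*Combined protocol and SAP*

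**What the plan says.** The document has a single section, Study Protocol and Statistical Analysis Plan, with a design paragraph and a statistics paragraph.

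- **Arms.** "the teeth will be assigned randomly to one of the 3 groups", with 40 teeth in each of formocresol, ferric sulfate and hyaluronic acid.
- **Assessments.** "The teeth will be followed clinically and radiographically at 1st, 3rd, 6th, 12th months".
- **Sample size.** "Sample size calculation showed that at first 40 teeth in each group will be required to detect a significant difference", at "80% power, two-sided 5% significance level". No outcome, visit, contrast or failure rate is attached to that difference.
- **Tests.** The statistics paragraph lists "the chi-square and Fisher exact test for the comparison of qualitative data", and adds that McNemar's "test will be used for time comparisons of qualitative data". It does not say whether arms are compared three at a time or in pairs, or at which visits.
- **Decision rule.** "The results will be evaluated at the significance level of" p<0.05, for all results alike.

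**The concern.** A comparative trial needs one result that was fixed in advance as the basis for its conclusion. Here there are 2 domains × 4 visits = 8 places to look for a medicament difference, and 8 × 3 pairs = 24 if the arms are compared two at a time. Each is judged at 0.05 and none is marked as the intended test. The sample size sentence might have identified it, but it does not.

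Two things follow. The chance of at least one false medicament difference can exceed 5% by an amount the plan does not control. And a reader who sees one p-value below 0.05 cannot tell whether it was the planned comparison or one picked from many.

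The plan does not promise to control the error over all tests together. Its two-sided 5% belongs to the sample size calculation, and p<0.05 is a per-test level. The fault is therefore an unprotected conclusion, not a broken guarantee.

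**Working it through.** **Inputs from the document:** 3 arms, 40 teeth per arm, 2 domains, 4 visits, two-sided 0.05, 80% power. **Inputs not in the document, assumed below:** failure rates, their timing, the dependence between domains, the family of tests, and one tooth per child (or independent teeth).

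**1. The plan's own figure.** Forty per arm cannot be reproduced, because no effect is stated. Working backwards, the standardised difference that 40 per arm detects is √2 × (1.960 + 0.842)/√40 = 0.626. For success proportions, 95% against 72% or 90% against 64% would also fit (pooled normal formula, no continuity correction). The calculation is compatible with many comparisons and so does not identify a primary one.

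**2. One domain at month 12, no true difference.** Exact enumeration of all 41³ possible outcomes for three arms of 40 independent teeth, with the same failure probability in each arm. The chi-square test is used unless an expected count is below 5, when the exact test replaces it.

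| Assumed failure | One three-arm (3×2) test | Any of three pairwise tests | Any of three pairwise, Fisher only |
|---|---|---|---|
| 5% | 2.7% | 1.1% | 1.1% |
| 10% | 4.1% | 6.6% | 4.4% |
| 15% | 4.6% | 11.4% | 6.6% |
| 20% | 4.9% | 12.2% | 7.2% |
| 25% | 5.0% | 12.1% | 7.3% |
| 30% | 5.0% | 11.7% | 7.1% |

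**3. Several visits and domains, no true difference.** Simulation with 40,000 trials per setting. Failures persist once they occur and accumulate in proportion to time (1/12, 3/12, 6/12 and all of the 12-month rate). Radiographic/clinical failure at 12 months is 10/5, 20/10, 20/15 or 30/15%, and the domains range from independent to nested. Chance of at least one false medicament difference:

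- Two 3×2 tests, both domains at month 12: 7.3–9.4% with chi-square, 6.1–9.4% if exact when sparse.
- Eight 3×2 tests, both domains at four visits: 10.6–23.3% with chi-square, 6.7–19.1% if exact when sparse.
- Twenty-four pairwise tests: 7.3–31.2% with Fisher when sparse, 5.1–20.7% with Fisher only.
- Rare failures (5/2.5%): 3.3–4.5% for eight tests exact when sparse, and 1.1–1.3% for 24 pairwise tests. Here there is no inflation.

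McNemar tests are not counted, because they concern change over time and not differences between medicaments.

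**4. A gated test.** The procedure is one 3×2 test at 0.05, followed by pairwise tests at 0.05 only if it is significant. With no true difference its error is the second column of the table. If two arms are equal and the third differs, the equal pair is falsely separated in 0.4–4.8% of trials in 12 scenarios. The figure reaches 5.2% and 5.7% when the equal arms fail at 40% and 50%, because the chi-square test is approximate.

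**5. Power for the largest contrast**, by the same enumeration:

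| Failure by arm | Ungated | Gated | Bonferroni (3 pairs) | Holm |
|---|---|---|---|---|
| 5/5/25% | 72.0 | 68.3 | 53.2 | 56.6 |
| 10/10/30% | 62.9 | 57.1 | 43.5 | 46.0 |
| 10/10/35% | 79.3 | 75.8 | 62.9 | 65.9 |
| 10/10/40% | 90.1 | 88.5 | 79.0 | 81.7 |
| 10/20/35% | 79.3 | 68.0 | 62.9 | 63.7 |
| 5/15/30% | 87.5 | 78.6 | 73.9 | 74.4 |
| 10/25/40% | 90.1 | 82.1 | 79.0 | 79.6 |

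The gate loses 1.6–5.8 points when two arms are alike and 8.0–11.3 when the third lies between. Bonferroni loses 11.1–19.4 and Holm 8.4–16.9.

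**6. Independence of teeth.** The unit is the tooth ("120 primary molar teeth from healthy children aged between 5 and 9"), and the number of children is not given. If 60 children gave two teeth each, with assumed within-child correlation 0.1–0.5 and failure 10–30%, the single 3×2 test has size 4–5% when each tooth is randomised separately. It is 5–14% when both teeth share an arm and 1–4% when they are split between arms.

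**The case against.** The plan breaks no rule of its own: it makes no confirmatory claim and no promise about the error over all tests together. The size of the harm rests on assumed failure rates, timing, dependence and families of tests, and the results run from about 1% to 31%, which includes no inflation at all. Fisher's test is on the plan's list and is conservative when failures are few. Neither the 8-test nor the 24-test family is stated in the plan. The gate is one valid choice among several, since a single named contrast or Holm's method would also close the gap. Teeth per child is a unit-of-analysis question, and the allocation sentence reads as tooth by tooth, for which the size is 4–5%.

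Much of this stands. The percentages are illustrations, no single inflation figure can be assigned to this trial, and the gate is a recommendation and not the only remedy. The clustering figures show only what the 5% depends on.

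The conclusion survives. The plan neither commits to Fisher's test nor gives failure rates, so it cannot rely on the favourable readings. Even one domain at one visit reaches 11–12% with ordinary pairwise tests at 15–30% failure. The freedom to choose the headline result afterwards exists at any failure rate.

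**Conclusion.** The concern holds. No outcome, visit or contrast is designated, and one unadjusted threshold governs everything, so the trial's conclusion about medicaments is not protected at 5%. With 12-month failure of roughly 10–30% and independent teeth, plausible readings of the plan put the chance of a false difference anywhere from about 4% to about 31%. A single three-arm test at month 12 would hold it at 4.1–5.0%. With rare failures and exact tests there may be no excess. The absence of a designated result can be read directly from the document and needs no assumption; the percentages do. This should be corrected, but it is not a fatal flaw.

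**What to change.** Before outcome data are compared, add to the statistics paragraph:

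1. One primary outcome (one domain, or a defined combined clinical and radiographic success) at one visit, for example month 12, the last planned one.
2. One 3×2 test of it across the three arms at 0.05, exact when an expected count is below 5.
3. The three pairwise tests at 0.05 only if that test is significant. With three arms this is a closed procedure and needs no further split of alpha.
4. A statement that the other domain, the other visits and the McNemar comparisons are secondary and carry no confirmatory claim.
5. Whether a child can contribute more than one tooth and, if so, how those teeth are allocated and handled in the primary test.

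The sample size sentence should refer to the same outcome and visit.

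The cost is a few sentences, the loss of confirmatory status for secondary results, and some pairwise power. At failure 10/10/35%, power for the largest contrast falls from 79.3% to 75.8%; at 10/20/35% it falls from 79.3% to 68.0%. In all seven scenarios examined the gate cost less than Bonferroni or Holm over the three pairs.
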